4.5.7 Patient-Reported Outcomes

To capture bleed and hemophilia medication use data, as well as HRQoL and health status data during study treatment, patients/caregivers will complete the Bleed/Medication questionnaires on an electronic, handheld device that will be provided to them during their Week 1 visit at the site. This device will remain with the patients/caregiver for the duration of the study to enter bleed and medication data on a weekly basis at minimum *before the study extension phase. After the start of the extension phase, bleed and medication data will not be collected.* Patients and/or caregivers will complete HRQoL, proxy HRQoL-SF, and aspects of caregiver burden questionnaires at designated timepoints during clinic visits on a separate electronic, handheld device (tablet) that will remain at sites. The electronic, handheld device and instructions for completing the questionnaires will be provided by the investigator staff. The questionnaires should be completed by the patient or their caregivers at the site at the start of the visit and prior to all other study assessments.

After bleed, medication, HRQoL, proxy HRQoL, and aspects of caregiver burden entries have been saved, the data will be transmitted automatically from the respective devices to a centralized vendor database. Bleed and medication use data entered since the

patient's previous clinic visit will be reviewed at subsequent clinic visits, as per the schedule of assessments, for completeness and accuracy. Investigators will review the bleed and bleed medication data as per the schedule of assessments (see [Appendix 1](#)) and have the ability to correct or complete entries once verified with the patient/caregiver using a Data Change Request Form process or via a Web-based portal, once implemented.

4.5.7.1 Health-Related Quality of Life

The Haem-A-QoL and the Haemo-QoL-SF (only for patients aged 8–17 years) will be used to measure HRQoL in adults and adolescents/pediatric patients, respectively (see [Appendix 2](#), [Appendix 3](#), and [Appendix 4](#), respectively). The Haem-A-QoL was designed for adult patients with hemophilia. It consists of 46 items comprising 10 dimensions (physical health, feelings, view, sport and leisure time, work and school, dealing, treatment, future, family planning, and relationships/partners) and a scale representing total score. Items are rated along 5 response options, although for some items there is also a “not applicable” option (von Mackensen and Gringeri 2005; 2010).

The Haemo-QoL-SF was developed as a series of age-related questionnaires to measure HRQoL in children and adolescents with hemophilia (Bullinger et al. 2002; von Mackensen and Bullinger 2004; Pollak et al. 2006). These versions include a 77-item long form, a 35-item as well as a 16-item short form, and an 8-item index form. The short version for older children containing 35 items was selected for this study. This version covers nine dimensions considered relevant for the children’s HRQoL (physical health, feelings, view of yourself, family, friends, other people, sports and school, dealing with hemophilia and treatment). Items are rated with five respective response options: never, seldom, sometimes, often, and always. Higher scores for both HRQoL measures are indicative of poorer HRQoL.

4.5.7.2 Health Status

The EQ-5D-5L (see [Appendix 5](#)) is a generic, preference-based health utility measure that assesses health status and is used to inform pharmacoeconomic evaluations, which will only be assessed for patients from Arms A, B, and C. The EQ-5D-5L consists of two parts. The first part, health state classification, contains five dimensions of health: mobility, self-care, usual activities, pain/discomfort, and anxiety/depression (Herdman et al. 2011; Janssen et al. 2013). Published weights are available that allow for the creation of a single summary score. Overall scores typically range from 0 to 1, although a score below 0 is theoretically possible representing a state worse than death, with low scores representing a higher level of dysfunction. The second part is a 0 to 100-point visual analog scale (VAS) that assesses current health status; higher scores are reflective of better health.

4.5.7.3 Adapted Inhib-QoL, Including Aspects of Caregiver Burden

Proxy assessment of HRQoL-SF and aspects of caregiver burden for all children, regardless of age, will be collected using the Adapted Inhibitor-Specific Quality of Life

(Inhib-QoL) with Aspects of Caregiver Burden questionnaire (see [Appendix 6](#)). This will be completed by caregivers as per the schedule of assessments during clinic visits (see [Appendix 1](#)).

4.5.7.4 Daycare/School Absences and Hospitalizations

All patients or their caregivers will be asked to report on an electronic, handheld device the number of days of daycare/school that were missed (if applicable). The number of days the child was hospitalized (if applicable) will be derived from data collected on eCRF.

4.5.8 Definition of a Bleed

For the purposes of the efficacy analyses, a standardized definition of bleed, adapted from criteria defined by the Subcommittee on Standards and Criteria, FVIII/FIX subcommittee of the International Society of Thrombosis and Hemostasis and similar to that used in a recent clinical study, will be used in this study (Blanchette et al. 2014; Mahlangu et al. 2014), which includes the following additional criteria:

- Bleeds starting from the first sign of bleed and ending 72 hours after the last treatment for the bleed, within which any symptoms of bleeding at the same location or injections are \leq 72 hours apart, are considered the same bleed.
- Any injection to treat the bleed, taken $>$ 72 hours after the preceding injection, is considered the first injection to treat a new bleed at the same location.
- Any bleed at a different location is considered a separate bleed regardless of time from last injection.

An additional definition of all bleeds (i.e., both treated and not treated with coagulation factors) will be applied for certain secondary efficacy analyses.

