## **2.3 ENDPOINTS**

### **2.3.1 Primary Efficacy Endpoint**

Bleed rate is defined as the number of bleeds over the efficacy period. A bleed is counted in the primary analysis if it was treated with coagulation factors and fulfills the adapted International Society on Thrombosis and Haemostasis (ISTH; [Blanchette et al. 2014](#)) criteria, as described in Section 4.5.8 of the protocol. More specifically, the following rules as outlined in the sections below are applied.

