### **2.3.1.2      Treated Bleed**

A bleed is considered to be a “treated bleed” if it is directly followed (i.e., there is not an intervening bleed) by a hemophilia medication reported to be a “treatment for bleed,” irrespective of the time between the treatment and the preceding bleed. A bleed and the first treatment thereafter are considered to be pairs (i.e., one treatment belongs to one bleed only), with the following exception: if multiple bleeds occur on the same calendar day, the subsequent treatment is considered to apply for each of these multiple bleeds (which are, however, counted as separate bleeds).

Bleeds due to surgery/procedure are not included in the primary analysis. Only treatments that were recorded as “treatment for bleed” are included in the determination of a treated bleed.

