### **72-Hour Rule**

Two bleeds of the same type (e.g., “joint,” “muscle,” or “other”) and at the same anatomical location are considered to be one bleed if the second occurs within 72 hours from the last treatment for the first bleed. The last treatment is defined as the last treatment before a new bleed occurs, either in the same or in a different location. This is in-line with the above definition that bleeds and treatments are considered to be pairs.

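### The SAP's counting rules can give a different primary-endpoint count from the protocol bleed definition they are said to apply, in either direction

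*Protocol*

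**What the plan says.** Protocol 4.5.8 defines a bleed for the efficacy analyses. A bleed runs from its first sign, "ending 72 hours after the last treatment for the bleed". Symptoms or injections at the same location no more than 72 hours apart belong to one bleed. An injection beyond that gap "is considered the first injection to treat a new bleed at the same location". For other sites: "Any bleed at a different location is considered a separate bleed regardless of time from last injection". Nothing there says that a bleed elsewhere closes the first one.

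SAP 2.3.1 says a counted bleed is a treated bleed that meets the adapted criteria "as described in Section 4.5.8 of the protocol. More specifically, the following rules as outlined in the sections below are applied". The rules that follow are these:

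- SAP 2.3.1.2: a recorded bleed is treated if a *treatment for bleed* follows before any other bleed, "irrespective of the time between the treatment and the preceding bleed". Apart from bleeds on the same calendar day, "one treatment belongs to one bleed only".
- SAP 72-Hour Rule: two recorded bleeds of the same type and location merge if the second starts within 72 hours of the last treatment for the first. "The last treatment is defined as the last treatment before a new bleed occurs, either in the same or in a different location".

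**The concern.** The SAP presents its rules as the specific application of Protocol 4.5.8 and declares no departure, yet they differ in two places.

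(a) **Late injections.** No SAP rule lets an injection open a bleed, and the last treatment is defined with no limit on the gap between successive injections. The protocol starts a new bleed at such a gap; the SAP carries on with the old one.

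(b) **A bleed at another site.** The SAP stops attributing treatments to the first bleed once any other bleed is entered. The protocol follows the treatments given for that bleed, whatever happens elsewhere.

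The treated-bleed count is the primary endpoint. The all-bleeds, joint, spontaneous and target-joint endpoints in SAP 2.3.2 use the same counting rules, and the first three are in the testing hierarchy of SAP 4.5.2. If the two documents count one diary differently, the reported rates and rate ratio cannot be traced to the protocol definition.

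**Working it through.** **The plan's own figure.** This point disputes no stated number, but the planned power gives scale. Inputs from Protocol 6.1: ABR 4 and 18, variance 10 × mean, 28 and 14 patients, 0.5 time units, two-sided 0.05.

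- Negative binomial dispersion: mean + k·mean² = 10·mean, so k = 9/mean, giving 9/4 = 2.25 and 9/18 = 0.5.
- SE² = (1/(4 × 0.5) + 2.25)/28 + (1/(18 × 0.5) + 0.5)/14 = 2.75/28 + 0.611/14 = 0.0982 + 0.0437 = 0.1419, so SE = 0.377.
- ln(18/4) = 1.504, and 1.504/0.377 − 1.96 = 2.03, giving power of 97.9%.

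Negative binomial regression simulation (800 runs each) gave 97.9% with fixed follow-up, and 97.0% with assumed follow-up of 0.46–1.0 year on emicizumab and 0.46 on control. The stated figure of more than 90% is reproduced.

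**Hypothetical diaries under both rule sets** (times in hours):

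- A: knee bleed at 0, injections at 1 and 121, no new entry.
- B: as A, plus a knee entry at 168, injected at 169.
- C: knee bleed at 0, injected at 1; elbow bleed at 48; treatment at 49 for both elbow and knee; knee entry at 96, injected at 97.
- D: as C, but the treatment at 49 is for the elbow only.

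| Diary | SAP | Protocol 4.5.8 | SAP 4.5.4: no 72-hour rule | SAP 4.5.4: treatment days |
|---|---|---|---|---|
| A | 1 | 2 | 1 | 2 |
| B | 1 | 2 | 2 | 3 |
| C | 3 | 2 | 3 | 3 |
| D | 3 | 3 | 3 | 3 |

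- A: 121 − 1 = 120 > 72, so the protocol opens a second bleed. The SAP has one entry.
- B: the protocol's second bleed starts at 121 and takes in the entry at 168 (168 − 121 = 47). Under the SAP the last treatment before that entry is at 121, so the 47-hour gap merges the recorded bleed into the first.
- C: under the SAP the knee's last treatment is at 1, its window ends at 1 + 72 = 73, and the entry at 96 is new. Under the protocol the knee was treated at 1, 49 and 97 (gaps of 48), and its window after the second treatment runs to 49 + 72 = 121, so it is one knee bleed plus the elbow.
- D: the protocol's knee window also ends at 73, so the counts agree.
- The last two columns count recorded entries (1, 2, 3, 3) and distinct days with a treatment (2, 3, 3, 3).

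**Scale, by assumption only.** The documents give no frequency for these patterns.

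- For (a) alone, suppose 5%, 10% or 20% of control bleeds carry such an injection and none on emicizumab. The planning ratio 4/18 = 0.222 becomes 4/(18 × 1.05) = 0.212, 4/(18 × 1.10) = 0.202 or 4/(18 × 1.20) = 0.185 under the protocol rule. In that setting the SAP count is the less favourable one to emicizumab.
- If counts shift by up to ±20% in each arm, the ratio runs from 3.2/21.6 = 0.148 to 4.8/14.4 = 0.333, and power from 99.8% to 84.5% (same formula, k = 9/mean). Equal proportional shifts leave 0.222.

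**The case against.** **The cross-reference may carry the late-injection rule in.** A counted bleed must fulfil 4.5.8, so the SAP might be merely silent. Diary B answers this: applied as written, the 72-Hour Rule merges a recorded bleed that the protocol places in a second episode. That is a different count, not missing detail.

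**The wording on elapsed time is not the contradiction.** A reader might infer that "irrespective of the time between the treatment and the preceding bleed" conflicts with the protocol's 72 hours. It does not. It concerns the interval from a bleed to its treatment, on which 4.5.8 sets no limit. The conflict lies in the last treatment having no maximum gap between injections.

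**The window itself is not shortened.** A reader might infer that a bleed elsewhere cuts the 72 hours short. A full 72 hours still runs from the last attributed treatment; only attribution changes. The count differs only if the first site is still being treated after the other bleed is entered, and same-day entries are excepted. This stands and limits (b).

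**Pairing may be a practical necessity.** The injection fields listed in SAP 2.2.1 are date and time, reason, type and dose, without the site treated. That is a fair reason for a convention, though not for presenting it as the protocol definition.

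**Safeguards exist.** Investigator and sponsor review of the diary (SAP 2.2.1) may turn some late injections into bleed entries. SAP 4.5.4 plans counts without the 72-hour rule and by treatment days. These test sensitivity to counting, but the table shows that neither reproduces 4.5.8.

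**Versions.** The SAP reproduces the synopsis of protocol version 3, and the protocol supplied is version 5. Whether 4.5.8 differed earlier cannot be checked; the current texts conflict.

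**Conclusion.** The point holds: the SAP is wrong as written, because it claims the 4.5.8 definition and applies rules that can count the same diary differently. The difference is one bleed too few in diaries A and B and one too many in C.

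A reader might infer that the SAP rules favour emicizumab. The documents do not support that. If both patterns fall mainly on the control arm, which is plausible at a planned ABR of 18 against 4 but not established, (a) works against emicizumab and only (b) works for it. Net direction and size cannot be derived.

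The significance conclusion is unlikely to change: power is 97.9% as planned and 84.5% at the worst end of an assumed ±20% shift. This rests on the planning rates and on reading the variance on the annual scale; reading it on the 24-week count would give about 84% before any shift. The reported bleed rates, the rate ratio and their traceability to the protocol are what is exposed.

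**What to change.** 1. **Late injections.** In SAP 2.3.1.2 and the 72-Hour Rule, state that a *treatment for bleed* logged more than 72 hours after the preceding one, with no bleed entry in between, starts a new treated bleed at the same location. End the chain of treatments for a bleed at any gap above 72 hours. Diaries A and B then give 2.
2. **Bleed at another site.** Keep the pairing rule in the primary count, but declare it as an operational departure from 4.5.8 because the site treated is not among the listed injection fields. Add a sensitivity analysis that also credits injections after the second bleed to the first site. It gives 2 in both C and D against 3 under pairing, so the two counts bracket the protocol's 2 and 3. Do not make this the primary rule: in D it would merge bleeds that 4.5.8 keeps separate.
3. **Alternative.** If the SAP rules are what is intended, amend Protocol 4.5.8 before analysis and report the count under the present 4.5.8 as a sensitivity analysis.

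The cost of items 1 and 2 is SAP wording and derivation code, using times and reasons already collected. The alternative adds a protocol amendment. Neither needs new data.

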4.5.8.1 Bleed Sites

- Target joints: defined as a major joint (e.g., hip, elbow, wrist, shoulder, knee, and ankle) into which repeated bleeds occur (frequency of \geq 3 bleeds into the same joint over the last 24 weeks prior to study entry)
- Joint bleeds: having an unusual sensation (“aura”) in the joint in combination with any of the following:
 - Increasing swelling or warmth of the skin over the joint
 - Increasing pain
 - Progressive loss of range of motion or difficulty in using the limb as compared with baseline
- Muscle bleeds (sites as per the Bleed and Medications Questionnaire)
- Other bleeds (sites as per the Bleed and Medications Questionnaire)

4.5.8.2 Bleed Types

In addition, the assessment of a bleed will be separated into spontaneous bleeds, traumatic bleeds, and bleeds related to procedure/surgery. Both spontaneous bleeds (i.e., the occurrence of hemorrhage where neither the patient nor a caregiver can identify a reason) and traumatic bleeds (i.e., hemorrhage occurring secondary to an event such as trauma, “strenuous” activity, or “overuse”) will be collected.

- Spontaneous bleeds: Bleeds will be classified as spontaneous if a patient records a bleed when there is no known contributing factor such as definite trauma, antecedent “strenuous” activity, “overuse,” or procedure/surgery. The determination of what constitutes “strenuous” or “overuse” will be at the discretion of the patient. For example, light jogging may be considered “non-strenuous” while sprinting may be considered “strenuous,” lifting of weights for a short period of time may be considered “moderate use” while repetitive weightlifting may be considered “overuse.”
- Traumatic bleeds: Bleeds should be classified as traumatic if a patient records a bleed when there is a known or believed reason for the bleed. For example, if a patient were to exercise “strenuously” and then have a bleed in the absence of any obvious injury, the bleed would be recorded as a traumatic bleed because, although no injury occurred, there was antecedent “strenuous” activity. Bleeds subsequent to injuries would certainly be classified as traumatic.
- Bleeds related to procedure/surgery: such as hematomas resulting from any surgeries or invasive procedures (e.g., tooth extractions, venipuncture, or SC drug administrations) or invasive diagnostic procedures (e.g., lumbar puncture, arterial blood gas determination, or any endoscopy with biopsy, etc.) would not be counted as bleeds. Bleeds related to procedure/surgery are not associated with any trauma except procedure/surgery-induced trauma.

Patients (or patient’s legally authorized representative) or their caregivers will complete an electronic Bleed and Medication Questionnaire whenever a bleed occurs, or at least weekly to confirm all bleeds have been recorded until the patient starts the study extension phase. *After the start of the extension phase, bleed and medication data will not be collected.* For each bleeding episode, they will provide information on the above topics as well as on the medication used to treat the bleed. Hemophilia medications that were taken will also be collected through the Bleed and Medication Questionnaire. In the event that the electronic Bleed and Medication Questionnaire is not available, a paper version of the Bleed and Medication Questionnaire may be used. The data will be reviewed by sites during site visits.

4.6 PATIENT, TREATMENT, STUDY, AND SITE DISCONTINUATION

4.6.1 Patient Discontinuation

Patients have the right to voluntarily withdraw from the study at any time for any reason. In addition, the investigator has the right to withdraw a patient from the study at any time. Reasons for withdrawal from the study may include, but are not limited to, the following:

- Patient withdrawal of consent at any time
- Any medical condition that the investigator or Sponsor determines may jeopardize the patient's safety if he or she continues in the study
- Investigator or Sponsor determines it is in the best interest of the patient
- Patient's inability or unwillingness to comply with protocol requirements, non-compliance despite appropriate education measures taken by the clinical site

Patients may elect to withdraw from the activity monitoring but continue participation in the remainder of the study. If a patient decides to withdraw only from the activity monitoring prematurely, the patient will continue treatment and follow-up as per the study protocol. The primary reason for withdrawal from activity monitoring should be documented on the appropriate eCRF.

Every effort should be made to obtain information on patients who withdraw from the study. The primary reason for withdrawal from the study should be documented on the appropriate eCRF. However, patients will not be followed for any reason after consent has been withdrawn. Patients who withdraw from the study will not be replaced.

4.6.2 Study Treatment Discontinuation

Patients must discontinue study treatment if they experience any of the following:

- Pregnancy

The primary reason for study treatment discontinuation should be documented on the appropriate eCRF. Patients who discontinue study treatment prematurely will not be replaced. Patients who become pregnant should immediately stop treatment and be managed as per local guidelines.

If the patient discontinues study treatment, bleed, hemophilia medication, HRQoL, health status, and missed days of school or work should be recorded by the patient on the electronic, handheld device until the safety follow-up visit (i.e., 24 weeks after the last study drug administration).

4.6.3 Study and Site Discontinuation

The Sponsor has the right to terminate this study at any time. Reasons for terminating the study may include, but are not limited to, the following:

- The incidence or severity of adverse events in this or other studies indicates a potential health hazard to patients.

- Patient enrollment is unsatisfactory.

The Sponsor will notify the investigator if the Sponsor decides to discontinue the study.

The Sponsor has the right to close a site at any time. Reasons for closing a site may include, but are not limited to, the following:

- Excessively slow recruitment
- Poor protocol adherence (e.g., bleed/medication questionnaire data not checked by investigator/co-investigator for >8 weeks)
- Inaccurate or incomplete data recording
- Non-compliance with the International Conference for Harmonisation (ICH) guideline for Good Clinical Practice
- No study activity (i.e., all patients have completed the study and all obligations have been fulfilled)

5. ASSESSMENT OF SAFETY

5.1 SAFETY PLAN

The safety plan for this study is designed to ensure patient safety and will include specific eligibility criteria and monitoring assessments as detailed below.

5.1.1 Patient Selection

The inclusion and exclusion criteria in this study are designed to select patients who are not at increased risk based on the current understanding of the investigational medication. See Section 4.1.1 and Section 4.1.2 for full inclusion and exclusion criteria, respectively.

